Varying methods of IANL and immediate implant placements that have used drills, burs, or saws have been reported [26, 27]. Disturbances in postoperative neurosensory function of the IAN are common. The risk of IAN morbidity created some controversy, which resulted in the limited use of this classic technique [28]. To tackle problems in edentulous instances, especially those with atrophic mandibles, various surgical procedures utilizing osseointegrated implants have been devised [29]. Onlay bone grafting, a prevalent approach, necessitates a secondary surgical site and entails hazards including graft resorption, infection, and the requirement for two surgical procedures, thereby prolonging the entire treatment duration [29-31]. The bone quality in the posterior mandible is generally lower than that of the anterior area. Utilizing short implants to circumvent the mandibular canal often results in initial implant anchorage that is monocortical and comparatively unstable [32].

The key benefits of IAN relocation encompass the utilization of standard-length implants with bicortical anchorage, hence augmenting primary stability, which is essential for effective osseointegration. Implants accompanied by nerve relocation have a reduced risk of bone loss when compared to short implants implanted under analogous conditions [33]. In instances when the vertical bone height is below 5 mm—insufficient for even small implants—IAN repositioning is the advised procedure [34]. This treatment enhances resistance to occlusal stresses and guarantees an appropriate implant-to-prosthesis connection. In comparison to bone grafting, IAN relocation presents multiple advantages: it can be executed under local anesthetic, eliminates the need for a donor site, incurs cheaper expenses, and is linked to diminished morbidity [14, 35]. The present study aimed to investigate the efficacy of the IANL procedure for dental implants in the atrophied mandibles.

Patients and Methods:

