This is a prospective randomized clinical trial. The study was carried out in patients with posterior mandibular atrophies among selected cases from patients attending Faculty of Dentistry dental polyclinics and some private dental clinics in Sana'a City from 10 July 2024 to 20 April 2025. The minimal calculated sample size was nine cases (G-power sample calculator; Effect size, 99.99; α err prob, 0.05; Power, 0.80; and Df, 7) [36]. The age of patients was above 18 years, according to [36]. Patients included in the study were those who have a bone height above the IAN that ranged from 0.5 to 7.0 mm and patients with bone width less than 5 mm in the planned dental implant sites. All patients were informed about alternative treatments and given information regarding all steps of the procedure, the risks of the surgery, and possible postoperative neurosensory dysfunction. All explanations were given to the patients verbally and in a written manner. Patients with active infections, uncontrolled diabetes, or a history of radiotherapy, chemotherapy, or oral cancer surgery were excluded from this study. Demographic data (name, age, gender, occupation, address, phone number, and habits) were collected using a preformed questionnaire. Present and past medical and dental history was also recorded for all patients. All patients received a thorough dental examination (extra-oral and intra-oral examination) in dental clinics using a dental mirror, ball-tipped WHO dental probe, and dental tweezers. Sterile examination tools by autoclave class B were used. Clinical examination included oral health and oral hygiene status, interarchdistance, dimensions of edentulous ridge, and soft tissue condition. Panoramic radiographs were taken to assess the condition of the patients' teeth and jawbone, as well as to detect any oral infections requiring treatment. These images also served as baseline documentation for comparison before and after treatment. CBCT revealed significant vertical and horizontal bone loss (bone quantity) and bone density (bone quality) in the mandibular premolar and molar areas, with the residual bone above the IAN ranging from 0.5 to 7.0 mm. All cases' mandibles were classified as class V (flat ridge form, inadequate in height and width) or class VI (depressed ridge form, with some basilar loss evident) according to the Howell-Cawood classification [5]. All patients were provided written

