Testing of nerve function and implant success rate during the scheduled follow-up visits was scheduled on the day after the procedure and at 1, 3, and 6 months immediately following the surgery [40]. Patients were asked about pain and neurosensory disturbance classified as positive (including paresthesia, dysesthesia, and hyperesthesia) or negative (such as hypoesthesia and anesthesia). The incidence and duration of neurosensory disturbance were evaluated by the light touch test using cotton or gauze. A cotton tip applicator is used to determine sensation (Static Touch Detection Tests), and a pinprick test is done with an insulin needle and the tip of an explorer probe at predetermined intervals of time. Neurosensory evaluation was carried out on the 1st and 7th postoperative days and every month thereafter for up to 6 months. The areas of impaired nerve function were mapped and followed during each follow-up appointment. The evaluation of nerve function was performed by two calibrated examiners. [34] The implant success rate was done by primary stability during insertion by ratchet, then X-rays (panorama and CBCT) were taken at 3 months and 4 months after implant insertion to check for marginal bone loss (MBL). The degree of osseointegration of the implants was determined by examining whether or not the implants were both painless and immobile when under torque and while

loading and whether or not any pathology was detected in the X-rays during the examination [34].

Abutments and prosthodontic procedures:

In this study, all patients received prosthetic rehabilitation using AnyRidge (MegaGen) implants with multi-unit abutments to ensure a predictable and efficient restorative phase. The multi-unit abutments, designed by the manufacturer, were selected based on implant angulation and soft tissue thickness, with both straight and angled options (15° and 25°) and various collar heights available to accommodate individual anatomical variations. These abutments helped standardize the prosthetic platform, simplify the restoration delivery, and improve long-term outcomes. All prostheses were cement-retained, except for one case where a screw-retained restoration was employed. The use of multi-unit abutments played a key role in managing implant angulation and facilitating a smooth and accurate prosthodontic alignment.

Data management and statistical analysis:

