All data were collected and then analyzed using statistical software (SPSS Version 27; SPSS Inc., Chicago, USA). Descriptive analyses were performed as frequency and proportion for categorical variables and the mean and standard deviation of quantitative variables. Analytical statistics were performed to find out the association between variables (demographic characteristics, neurosensory disturbance, and success rate of implant) with IANL. Non-parametric tests were done to measure the differences between pre- and post-times of operation (Fridman and Wilcoxon tests). $P < 0.05$ was considered statistically significant.

List of Abbreviations:

Abbreviations

Definition

IAN

Inferior Alveolar Nerve

IANL

Inferior Alveolar Nerve Lateralization

IANT

Inferior Alveolar Nerve Transposition

RRR

Residual Ridge Resorption

CBCT

Cone Beam Computed Tomography

ND

Neurosensory Disturbances

MC

Mandibular Canal

PRF

Platelet-Rich Fibrin

MBL

Marginal Bone Loss

Declarations:

Ethics approval and consent to participate: The study design adhered to the tenets of the Declaration of Helsinki and was approved by the Medical Research Ethics Committee in the Faculty of Medicine at Sana'a University; ethical approval was obtained (Approval Number: OMFS:14/06/2024). Detailed explanation of the procedures was provided for all participants. Verbal and written consent were obtained from all participants; all patients agreed to be involved in the study.

Clinical trial number: not applicable.

Consent for publication: NA

Availability of data and materials: The authors confirmed that the raw data that support the findings of this study are available from the corresponding author upon reasonable request.

Competing interests: The authors declare that they have no competing interests.

Funding: The study was self-funded by the authors.

Authors' contributions: HS & YA performed the surgical interventions and collected data from the patients and drafted the manuscript. MA performed the conceptualization of the study and was a major contributor in writing the manuscript. YA, AA, and TA revised the clinical work and the draft manuscript. All authors read and approved the final manuscript.

Acknowledgements: the authors thank all the patients included in the study as well as the Department of Oral and Maxillofacial Surgery in the Faculty of Dentistry, Sana'a University.

References:

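### The aim is efficacy of nerve lateralization, but the only named tests compare time points; on neurosensory disturbance they would measure recovery from a complication, not efficacy or residual harm

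*Combined protocol and SAP*

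**What the plan says.** The Background ends with the aim: "The present study aimed to investigate the efficacy of the IANL procedure for dental implants in the atrophied mandibles". The same section treats nerve disturbance as a consequence of the surgery: "Disturbances in postoperative neurosensory function of the IAN are common".

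Patients and Methods opens with "This is a prospective randomized clinical trial", but only one operation is described, with no control group or allocation ratio. The minimum sample size is nine.

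Post-operative follow-up states: "The incidence and duration of neurosensory disturbance were evaluated by the light touch test using cotton or gauze". It places nerve testing on days 1 and 7 and then monthly to month 6. An earlier sentence of that section lists the day after surgery and months 1, 3 and 6, for implant success as well as nerve function. Both schedules are wholly postoperative; no preoperative neurosensory test is described. X-rays for marginal bone loss are at 3 and 4 months.

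Data management and statistical analysis plans counts and percentages for categorical data, then: "Analytical statistics were performed to find out the association between variables", covering demographics, ND and implant success in relation to IANL, with no test named. The only named tests follow: "Non-parametric tests were done to measure the differences between pre- and post-times of operation (Fridman and Wilcoxon tests". No outcome is given for them. P below 0.05 "was considered statistically significant".

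**The concern.** An efficacy question needs either a contrast with another treatment or a clearly defined success outcome with its uncertainty. The named tests supply neither. The association analysis does not fill the gap, because every described patient has IANL and there is nothing to contrast it with.

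ND is the outcome with the fullest repeated schedule, so it is a natural candidate for Friedman and Wilcoxon tests. Its course is injury at surgery followed by possible resolution. A significant change between postoperative visits would show that some patients recovered. It would not show that the procedure works for implants, nor how many patients are left with a deficit. A report could then carry a p-value below 0.05 that looks favourable to the operation, while the figure that matters for risk, the share with ND at month 6, has no interval and no stated role.

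**Working it through.** **Inputs.** N = 9 is the plan's minimum sample size, used here only as the size of the illustration. It cannot be reproduced from the stated inputs (an effect size of 99.99 gives N = 2 for a paired t test), but nothing below depends on how nine was reached. The documents give no ND incidence or recovery rate, so the series below are assumed. ND is simplified to present/absent per patient, with no new ND after day 1.

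**Test.** Compare day 1 with month 6. With binary data all non-zero differences have the same size, so the Wilcoxon signed-rank test reduces to a sign test on the k patients who change. If all k improve:

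- exact two-sided p = 2 × 0.5^k
- asymptotic z = √k

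The plan names SPSS but not which version of the test, so both are shown.

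| ND day 1 → month 6 | k | Exact p | Asymptotic p | Still affected at month 6 |
|---|---|---|---|---|
| 9/9 → 3/9 | 6 | 2 × 0.5^6 = 0.031 | 0.014 | 3/9 = 33% |
| 6/9 → 0/9 | 6 | 0.031 | 0.014 | 0/9 |
| 9/9 → 5/9 | 4 | 2 × 0.5^4 = 0.125 | 0.046 | 5/9 = 56% |
| 4/9 → 0/9 | 4 | 0.125 | 0.046 | 0/9 |
| 3/9 → 0/9 | 3 | 2 × 0.5^3 = 0.25 | 0.083 | 0/9 |
| 0/9 → 0/9 | 0 | 1 | 1 | 0/9 |

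Rows 1 and 2 have the same p-value with three patients impaired and with none. Rows 3 and 4 repeat this with five and none. The test sees k and nothing else. Injuries matter because they cap k: the exact test needs k ≥ 6 (k = 5 gives 0.0625) and the asymptotic test k ≥ 4, so a series with three or fewer injured patients cannot reach significance by either.

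**Chance of significance.** Assume each injured patient recovers with probability 0.7 by month 6. The exact test then needs at least 6 recoveries among m injured: 0 for m = 3, 0.7^6 = 0.118 for m = 6, and 0.730 for m = 9. For m = 9 the range is 0.254 (recovery probability 0.5) to 0.992 (0.9).

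**Comparison with a preoperative state.** Suppose all nine are taken as intact before surgery. Wilcoxon against month 6 then counts patients worsened: 6 with persistent ND gives p = 0.031 in the direction of harm. Friedman has no direction. With that zero baseline, visits at day 1 and months 1, 3 and 6, and nobody recovering, it is significant from 3 injured patients (p = 0.017). Neither result addresses efficacy.

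**What an estimate would show.** Exact (Clopper-Pearson) 95% intervals for ND at month 6:

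- 3/9: 7.5 to 70.1%
- 5/9: 21 to 86%
- 0/9: 0 to 1 − 0.025^(1/9) = 33.6%

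**The case against.** The strongest reply is that the plan never says these tests are for ND. Its wording refers to times before and after the operation, ND has no preoperative assessment, and the one before/after comparison described in Patients and Methods is radiographic. That stands, and the point is therefore conditional. The radiographic reading is not a clean fit either: marginal bone loss around an implant has no preoperative value, and its X-rays are at only two times, whereas Friedman is for three or more.

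A second reply is that the plan already provides percentages and measures ND incidence and duration to month 6. That also stands. The month-6 proportion is obtainable; what is missing is its interval and its role as a safety result.

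Four stronger readings are tempting, and the documents do not support them:

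- That more nerve injury in itself makes a significant improvement easier. Significance follows recoveries. Injuries only make them possible, and the chance rises with injuries only if the recovery probability does not fall.
- That only the worst series would be significant. Four recoveries with nobody left impaired give p = 0.046 by the asymptotic test, and 6/9 → 0/9 is significant by either.
- That the plan presents falling ND as proof of efficacy. No section says so, and implant success is a separate outcome.
- That recovery is unaided. This is not stated, and Post-operative care allows methylcobalamin. Some recovery, from any cause, is all the argument needs.

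**Conclusion.** The concern holds in conditional form. The named tests compare time points, have no stated outcome, and cannot answer an efficacy question in a study that describes one operation and no comparator. Applied to postoperative ND, they test resolution of a complication and are blind to residual impairment: in the nine-patient illustration, p = 0.031 goes equally with 33% still affected and with none. Applied against an assumed intact preoperative state, they would show worsening. The size rests on N = 9, binary ND, no new cases after day 1, and assumed incidence and recovery. The blindness to residual harm does not depend on the assumed rates. The change is worth making because it alters what the report can conclude.

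**What to change.** In Data management and statistical analysis:

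1. Name the outcome and visits for each Friedman and Wilcoxon test, and state that time-point tests on ND are not evidence of efficacy.
2. Report ND as a safety result: the number and proportion of patients with any ND at day 1 and at month 6, each with an exact (Clopper-Pearson) 95% interval. Show the visit-by-visit course descriptively.
3. Base the statement on the procedure's performance on implant success with its own interval, either at patient level or with a method that allows for several implants per patient. Use the month-6 clinical assessment together with the scheduled 3- and 4-month X-rays; no month-6 X-ray is planned, so success at month 6 can only be clinical.
4. Word that result as a single-arm estimate. Without a comparator it describes outcome and does not establish comparative efficacy.

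This takes a few sentences and uses assessments already scheduled. The downside is that a possible significant p-value is given up and the intervals will be wide: even no ND at month 6 in nine patients leaves an upper limit of 34%.

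### Friedman and Wilcoxon tests share a flat P<0.05 with no primary contrast, no adjustment and no rule linking them; at nine patients, 4 to 8 before-after contrasts carry roughly a 12-22% false-positive risk per sensory test

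*Combined protocol and SAP*

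**What the plan says.** Under Data management and statistical analysis, the plan states: "Non-parametric tests were done to measure the differences between pre- and post-times of operation (Fridman and Wilcoxon tests"). A P value below 0.05 "was considered statistically significant", with no exception or adjustment. The section also announces association tests: "Analytical statistics were performed to find out the association between variables (demographic characteristics, neurosensory disturbance, and success rate of implant) with IANL".

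Under Post-operative follow-up, testing of nerve function and implant success is "scheduled on the day after the procedure and at 1, 3, and 6 months immediately following the surgery", which makes 4 assessments. Later in the same paragraph: "Neurosensory evaluation was carried out on the 1st and 7th postoperative days and every month thereafter for up to 6 months". That makes 8 (days 1 and 7, then months 1 to 6). On the measures, "The incidence and duration of neurosensory disturbance were evaluated by the light touch test using cotton or gauze"; a cotton-tip static touch test and a pinprick test are added. None is called primary, and no pre-operative sensory test is described, although the analysis is of change from before to after surgery.

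Under Patients and Methods: "The minimal calculated sample size was nine cases (G-power sample calculator; Effect size, 99.99; α err prob, 0.05; Power, 0.80; and Df, 7").

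**The concern.** The error rate depends on four things that the plan leaves open: how many Wilcoxon contrasts are run, against which visit, on which sensory test, and whether a significant Friedman test must come first. The only stated rule is a threshold for each single test. Applied to several visits and several sensory tests, that rule does not keep the chance of a false finding at 5%.

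A reader could therefore be told that sensation differed from the reference at some month when that one result is chance. With nine patients there is little other evidence to set against it. Because no contrast is primary, the reader also cannot tell which p-value answers the trial's question.

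**Working it through.** **Plan's own figures.** The plan states no family-wise error rate, so there is none to reproduce. Its sample size is tied to no named test or contrast. Taken as written, an effect size of 99.99 gives power 1.0 at nine cases, so it does not lead to nine at 80% power. I take n = 9 only as the stated minimum.

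**Inputs from the documents.** n = 9; threshold 0.05; 4 or 8 post-operative visits.

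**Assumptions, because the documents are silent.** Two-sided exact Wilcoxon signed-rank tests, untied normal scores, one reference time plus the post-operative visits, and serial (AR(1)) correlation between visits of 0, 0.5 or 0.8. There were 40,000 simulated trials per case. All results are for one sensory test.

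**Step 1: a single contrast.** At n = 9 without ties, the exact two-sided p-values start at 2/512 = 0.0039, then 4/512 = 0.0078 and 6/512 = 0.0117. The largest below 0.05 is 20/512 = 0.0391. One contrast therefore has a true error of 3.9%.

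**Step 2: several contrasts, bound by formula.** If the tests were independent, 1 − (1 − 0.0391)^4 = 14.7% and 1 − (1 − 0.0391)^8 = 27.3%. Contrasts that share a reference visit are positively related, so the true values are lower.

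**Step 3: simulation.**

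| Chance of at least one false result (correlation 0 / 0.5 / 0.8) | 4 visits | 8 visits |
|---|---|---|
| No true change, each visit against the reference, no Friedman condition | 13.0 / 12.4 / 11.8% | 21.9 / 20.3 / 18.2% |
| No true change, same contrasts, only after Friedman p<0.05 | 2.9 / 3.3 / 3.7% | 3.0 / 3.8 / 5.1% |
| Only day 1 truly differs (large shift), other contrasts with the reference, after Friedman p<0.05 | 10.3 / 9.7 / 9.1% | 19.8 / 17.8 / 15.8% |
| No true change, all pairs, no Friedman condition (10 or 36 pairs) | 26.1 / 25.5 / 24.0% | 57.4 / 54.5 / 49.8% |

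All pairs after a significant Friedman test, with no true change, gave about 4-8%. In the third row Friedman rejected in every run, so it no longer restrained the other contrasts. That row matters because the Background itself describes postoperative sensory disturbance as common, so an early change is plausible.

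**Step 4: coarse scores.** The same reference contrasts, with no true change, unchanged patients dropped and 4,000 runs per case, gave with exact p-values at most about 4% for a binary score and about 2-10% for a three-level score. With normal-approximation p-values the figures were about 3-28% (binary) and 11-22% (three-level).

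**Step 5: what adjustment allows.** Holm's first threshold is 0.05/4 = 0.0125 for 4 contrasts and 0.05/8 = 0.00625 for 8. At n = 9, the three smallest exact p-values pass 0.0125, but only 0.0039 passes 0.00625. That needs all nine patients to change in the same direction. If one patient is unchanged, eight differences remain and the smallest p is 2/256 = 0.0078, which fails. For 36 pairs the threshold is 0.0014, which no result can reach.

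**The case against.** Three points on the other side carry weight.

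First, the statistics section speaks of differences between pre- and post-operative times, not of every visit against every other. A reader might infer all-pairs testing and take its range of about 18-58% (from 6 pairs among four visits to 36 pairs among nine time points) as this plan's error rate. The documents do not support that. They give no number of contrasts, and the before-after wording points to at most 4 or 8 per sensory test.

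Second, Friedman is named in the same sentence and may be meant as a first step. If so, the error is about 3-5% when nothing changes, which is acceptable. This stands for that case only: the plan does not state the order of testing, and the protection is lost once one visit truly differs.

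Third, the outcomes described are presence of disturbance, positive or negative type, and response to touch or pinprick, not continuous scores. Coarse scores with exact p-values bring the inflation down and can remove it. This also stands, but the plan does not specify the scale or the p-value method, and normal-approximation p-values bring the inflation back.

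Nor do the documents show that any one visit's p-value will be presented as the main result. The point is that nothing in the plan prevents it.

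**Conclusion.** The concern holds in conditional form. What is certain from the text is that there is one flat threshold, no primary measure, time point or contrast, no adjustment, no stated link between Friedman and Wilcoxon, and two visit schedules.

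The size depends on the reading. With n = 9, exact two-sided tests, untied scores and visit correlation of 0 to 0.8, it is about 12-13% (4 reference contrasts) or 18-22% (8) per sensory test without a Friedman condition. With that condition it is about 3-5% if nothing changes, and about 9-10% or 16-20% among the unchanged contrasts once day 1 differs. Testing more than one sensory measure adds to this. All-pairs testing would reach about 58%, but the plan does not say that it does this, so that figure is not a finding about this trial.

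**What to change.** 1. Reconcile the two follow-up schedules and define the reference visit. If no pre-operative sensory test was done, say so and state what the before-after comparison uses.
2. Name one primary neurosensory measure, with its scale, and one primary contrast: 6 months against the reference visit, tested at 0.05. State that p-values are exact.
3. Limit other Wilcoxon tests to each visit against the same reference. Either Holm-adjust them within each sensory test or report them as exploratory, without claims of significance. Do no all-pairs testing.
4. State the role of Friedman. It should not be offered as the only protection against multiple testing.
5. If outcomes have already been seen, disclose these choices as post hoc.

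The cost is text in the statistics and follow-up sections, with no new data. The primary contrast needs no adjustment. The secondary contrasts do lose power: with 8 of them, the first Holm step is met only if all nine patients change in the same direction, so those visits are in practice descriptive. With 4 contrasts there is a little more room.
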